## JHM IRB - eForm A – Protocol

\*\*\*\*\*

### 1. Abstract

Breast cancer is the most common cancer among survivors in the US and is second only to lung cancer in contributing to cancer death among women. Most patients with breast cancer receive help from family in making complex decisions about treatment, handling logically demanding care coordination, and managing symptoms and side effects. Although family members (as defined by each patient) play a vital role in cancer care, they are not formally recognized or assessed in care delivery, and their need for information and support is typically unmet. Lack of attention to family in care delivery is an important gap that too often leaves families without adequate information about patient health and treatments. This may prevent families and patients from engaging in open conversations, cause them unnecessary anxiety, and negatively affect the quality of cancer care and delivery.

Communication is particularly important in cancer care, as the optimal course of action is determined through longitudinal discussion of prognosis, treatments, and patient goals, preferences, and concerns. Strategies to improve communication for serious illnesses such as cancer have been developed, but typically target a specific decision, conversation, or setting, most often the inpatient hospital. There is growing agreement that communication among patients, families, and providers should be initiated early and continue throughout the disease trajectory. However, little is known about how to provide *both* patients *and* families with access to timely information about patient health and mechanisms to communicate directly with health care providers, as proposed in this study.

The goal of this study is to test a multicomponent intervention to strengthen communication and longitudinal partnerships among women with breast cancer and their family members. Recent work by the study team has demonstrated the feasibility, acceptability, and benefit of intervention components which will be combined into a single model of care. Our preliminary studies indicate that clarifying patient and family expectations regarding the role of family and providing family with timely and comprehensive information about patient health (as desired by the patient) leads to more effective family involvement, more frequent patient-familyprovider interactions, more patient-centered communication, and greater preparedness to manage care.

This study will evaluate the feasibility of delivering a multicomponent communication intervention in the outpatient setting comprising: 1.) a patient-family agenda-setting checklist completed immediately before a regularly scheduled medical oncology visit with a participating medical oncologist, 2.) facilitated registration for the patient portal (for patient *and* family member, as desired by the patient), and 3.) education (as relevant) on access to doctor's electronic visit notes. We will enroll up to 70 patients who are in active treatment for breast cancer. We will enroll up to 14 medical oncologists and 70 patient-family members. We will focus on patients who typically attend medical oncology visits with a family member or trusted friend as they are already present and involved in communication. We will compare study outcomes of patients and family members who are in the intervention group and receive the multicomponent communication intervention (n=35 dyads) with patients and family members who are in the control group and receive usual medical oncology care (n=35 dyads). We are asking whether intervention group patients and families have higher quality communication with medical oncology providers, a better understanding of patient's cancer, are more confident in managing patient's care and are more satisfied with cancer care than control group patients and families after 3 months, and 9 months of follow-up. We will also examine symptoms of anxiety.

### 2. Objectives

We will conduct a two-group randomized pilot trial of a multicomponent communication intervention to strengthen communication and longitudinal partnerships among up to 70 patients being actively treated for

breast cancer (early or advanced stage) and their family “caregiver” in an academic medical oncology clinic at Johns Hopkins. The intervention arm comprises: 1.) a patient-family agenda-setting checklist to be completed immediately before a routinely scheduled medical oncology visit, 2.) facilitated registration for the provider-sponsored patient portal (for the patient *and* family member, as desired by the patient), and 3.) education (as relevant) on access to doctor’s electronic visit notes. The control arm comprises usual medical oncology care. We will compare the intervention arm and a control arm of usual care with respect to patient and family-reported outcomes at 3 months and 9 months. We expect that patients and families who receive the intervention will engage in more frequent, higher quality communication with each other and medical oncology providers, and that 3 months and 9 months after enrollment patients and families will have a greater understanding of the patient’s illness, higher self-efficacy with respect to their ability to manage the patient’s care, and that families will be more highly satisfied with the quality of cancer care as compared with participants who receive a control arm of usual care. We will secondarily assess the effects of the intervention on patient and family symptoms of anxiety at 3 months and 9 months.

3. **Background:** This study will evaluate the feasibility of delivering a multicomponent communication intervention in the outpatient setting comprising: 1.) a patient-family agenda-setting checklist completed immediately before a regularly scheduled medical oncology visit, 2.) facilitated registration for the patient portal (for patient *and* family member, as desired by the patient), and 3.) education (as relevant) on access to doctor’s electronic visit notes. In the text that follows we summarize available evidence regarding each of the three intervention components.

**3a. Agenda Setting:** The study team has designed and established proof-of-concept for a patient-family agenda-setting checklist for older primary care patients. The checklist aims to elicit and align patient and family perspectives regarding issues to discuss with the doctor, and to stimulate discussion about the role of the family member in the visit. The premise for the checklist is that family members are typically motivated to support patients during medical visits, but that they often lack knowledge of the patient’s health concerns and visit goals as well as preferences for communication assistance from their family. The checklist involves two activities that are completed by a patient and their family member in the waiting room before a scheduled appointment. The **first** activity involves patients clarifying the help they would like from their family member during the upcoming visit. The **second** activity involves patients and families completing a checklist of common health issues. The instructions ask patient and family to separately identify their concerns for each issue, and decide together what to discuss with the doctor. In a proof of concept randomized study of 32 older patient-family dyads in a primary care setting, the checklist was highly endorsed by patients, families, and doctors. Analyses of audiotaped medical visits indicated that communication was significantly more patient-centered among dyads who completed the checklist (n=17) as compared with those who received usual care (n=15), and did not receive the checklist. In post-visit surveys, doctors were 34% more likely to agree that intervention versus usual care families “helped them provide good care to the patient” (94.1% vs. 60.0%; p=0.02). Intervention patients were more likely than usual care patients to agree that because their family was present they “better understood their doctor’s advice and explanations” (82.4% vs. 46.7%; p=0.03). *As the checklist was developed for older primary care patients, we have refined the content to attend to the specific needs of patients with breast cancer (see attachment D1 Checklist).*

**3b. Shared Access to the Patient Portal.** Health information technology presents new opportunities to rationalize and better support family in delivery processes and communication, as we propose in this study. Through the provider-sponsored patient portal, patients may access information about their health and treatments, exchange electronic messages with providers, and perform health care tasks such as refilling prescriptions and scheduling appointments. Many electronic health record vendors, including EPIC MyChart as implemented at Johns Hopkins, afford patients the ability to authorize specific family member to “share access” to their patient portal account using their own identity credentials. Thus, shared access is a strategy that may be used to clarify and respect patient preferences for including family in their care by facilitating access to the patient’s electronic health information and a mechanism to communicate directly with providers. Although little empirical evidence exists regarding the effects of shared access, work by our team indicates that shared access is acceptable to patients and families, and that family members who have

been granted their own identity credentials to access the patient's portal account commonly perform health management activities electronically and engage in secure messaging with providers.

**3c. Access to Provider's Visit Notes (OpenNotes).** Many electronic health records (including EPIC MyChart) have the capacity to allow providers to share their visit notes (OpenNotes) through the patient portal so that patients may read, reflect, and discuss these notes with family or other medical professionals after the visit. In a quasi-experimental pilot study involving more than 100 providers and 18,000 patients at 3 medical institutions, OpenNotes was found to improve patient-provider communication and increase patient engagement in their care. More than 10 million patients across the country are estimated to have access to their provider's visit notes. At some organizations, OpenNotes is standard practice among primary and specialty providers, including medical oncology. Preliminary studies provide evidence of the feasibility and acceptability of sharing doctor's electronic visit notes with *both* patients *and* families through shared access to the patient portal. After 12 months of having access to OpenNotes, the majority of patients and families read doctor's visit notes, reported clinically relevant benefits, and wanted to continue to have access to OpenNotes in the future. Patients and families reported that joint access led to more productive discussions about the patient's care, better agreement about the patients' treatment plan, and improved their ability to formulate questions for the doctor. Families were more likely to access and use the patient portal and reported better communication with doctors, while patients were more confident in their ability to manage clinically important elements of their care. OpenNotes has now been piloted through three stages of physician adoption at Johns Hopkins, including oncology providers, with high acceptability among providers and no reported adverse outcomes. The Johns Hopkins Clinical Practice Association's Board of Governors voted in early June to move toward system-wide standard access to OpenNotes across most lines of business, including ambulatory oncology effective January 1 2018.

#### 4. Study Procedures

**a. Study design, including the sequence and timing of study procedures** This is a two-group randomized pilot trial of a multi-component communication intervention to more effectively and purposefully engage family members in cancer care. We will enroll up to 70 patients with breast cancer and the family member they identify as most typically attending medical oncology visits with them, for a total of 70 patients and 70 family members. After providing informed consent, each patient-family member dyad will be randomized to the intervention arm or to a control arm of usual care.

We will invite practicing breast cancer medical oncologists at Johns Hopkins to participate in the pilot trial. We expect to enroll up to 14 medical oncologists in this study. As noted in Section 3.c., JHMI is moving toward system-wide use of OpenNotes effective January 1 2018. Participating providers will be invited to turn Open Notes "on" for patients under their care prior to January 2018, and the study team will record the decision made by each provider. Patient/family participants of providers who do not elect to turn "on" OpenNotes prior to January 2018 will receive agenda-setting checklist and facilitated access to MyChart but will not have education about or access to OpenNotes. We will mail letters to established patients of participating doctors who have a scheduled appointment two to four weeks prior to their visit to explain the study, invite them to participate, and invite family members to call us for more information. Patients who do not "opt-out" by mailing back a card to the study team will be contacted by telephone to further describe the trial, answer questions, and complete a screening call. Patients who are eligible and interested in participating will be asked to speak with their family member about the study in cases where the family member has not yet initiated contact with the study team. After the patient has discussed the study with their family member, the patient will ask the family member to call the study team, or given the family member's permission, the patient can call the study team with the family member's contact information. Both the patient and family must consent to participate for the dyad to be enrolled. Patients may identify more than one family member to participate in the intervention processes, but will be asked to identify the person who most typically attends medical oncology visits to participate in this study.

Eligible patient-family dyads will meet a member of the research team in the clinic waiting room 30 minutes in advance of the patient's scheduled appointment. Each dyad will be randomized to the intervention (investigational arm) or the control arm in a 1:1 ratio using stratified, blocked randomization by doctor with alternating block sizes. Participants assigned to the intervention will meet with the

research staff to receive a copy of the patient-family agenda-setting checklist, a clipboard and pen, and instructions describing how to complete the checklist, which they will complete together in the clinic waiting room. Participants who are randomized to the control arm will receive care as usual. Medical oncologists, patients, and families will complete post-visit surveys immediately after the visit. After the visit, patients in the intervention group will meet briefly with research staff to facilitate registration for the EPIC patient portal MyChart, including informational handouts about OpenNotes (as relevant) and MyChart. After the visit, participants in both groups will be offered general breast cancer resource handouts that are available to all breast cancer patients at the Johns Hopkins SKCCC. Patients and families will complete baseline, 3-month and 9-month follow-up telephone interviews by a research assistant who is blind to assignment status. Telephone interviews will be audio recorded for quality control purposes. Patients who decline audio recording will not be excluded from the study. Medical oncologists will complete an exit interview upon completion of patient recruitment.

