**b. Study duration and number of study visits required of research participants.**

Medical oncologist participation in the study will occur throughout the duration of recruitment.

Immediately after providing informed consent, medical oncologists will be asked to complete a one-page survey of socio-demographic characteristics, training, and experiences in the care of persons with breast cancer. Medical oncologists will subsequently complete a brief one-page survey immediately after the visit of participating patients, and a one-page exit survey upon completion of patient recruitment for the study. Patient and family participation in this study will transpire over no longer than 26 weeks, and will involve a screening telephone call to determine eligibility, one in-person encounter at the time of a regularly scheduled physician office visit, and two follow-up telephone calls of approximately 30 minutes duration at 1 weeks (range: 0-3 weeks), 3 months (range: 10-20 weeks) and 9 months (range: 3555 weeks). The in-person encounter is not expected to require more than 45 minutes time beyond the regularly scheduled physician visit. Participants will provide written consent to participate in the study (10 minutes) complete a pre-visit communication tool (10 minutes), and complete a brief post-visit survey (10-15 minutes). The expected duration of the study from the perspective of patient and family participants will proceed over the course of about 16 weeks (but may transpire over a longer period for some participants who are unavailable to complete the follow-up calls at the scheduled 16 week interview); the duration of the study for medical oncologist participants will proceed throughout the course of patient/companion enrollment. The overall study duration is expected to be about 12 months.

**c. Blinding, including justification for blinding or not blinding the trial, if applicable.** This is a single blind, two group randomized trial where the study team will be blinded to group assignment. Outcome measures will be assessed by interviewers masked to treatment assignment and without interventionist contact. Patient/family dyads will not be blinded to group assignment.

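### Does withholding OpenNotes education from dyads of doctors who open their notes late undermine the three-component intervention?

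*Combined protocol and SAP*

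**What the plan says.** The Abstract and Section 2 (Objectives) name three components: the agenda-setting checklist, facilitated portal registration, and "education (as relevant) on access to" the doctor's visit notes. The third is conditional from the start.

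Section 3c reports a vote, in early June of an unstated year, to "move toward system-wide standard access to OpenNotes across most lines of business, including ambulatory oncology effective January 1 2018". Section 4a repeats that date and invites participating doctors to open their notes sooner. It adds that "the study team will record the decision made by each provider". Dyads of doctors who do not open early "will receive agenda-setting checklist and facilitated access to MyChart but will not have education about or access to OpenNotes". The checklist and portal help belong to the intervention arm, so in context the rule concerns intervention dyads.

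The teaching takes place in a short meeting after the index visit, "including informational handouts about OpenNotes (as relevant) and MyChart". Section 4b provides for "one in-person encounter at the time of a regularly scheduled physician office visit"; the remaining contacts after the visit are telephone interviews. Under Section 4c, "Outcome measures will be assessed by interviewers masked to treatment assignment and without interventionist contact". Randomization is 1:1 by "stratified, blocked randomization by doctor with alternating block sizes".

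**The concern.** The rule in Section 4a has no end date, yet the protocol expects the condition behind it to lapse on 1 January 2018. An intervention dyad of a declining doctor, seen in autumn 2017, would leave the index visit with no OpenNotes handout. Its notes would then open during follow-up, and nothing in the plan provides for teaching it at that point. Read literally, the rule would also exclude that doctor's dyads seen after January 2018, when notes are already open.

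The stake is how the pilot's results are interpreted. Section 7c uses effect sizes to help design and size a larger trial. If that trial runs with notes open throughout, every intervention dyad would be eligible for all three components. Pilot effect sizes from a mixture of two-component and three-component dyads would then describe a somewhat weaker package. Section 7c also lists no count of how many dyads received each component.

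**Working it through.** The plan gives no figure to reproduce here: 70 dyads is a pragmatic number, with no power calculation. The check is date arithmetic, a bound on the number affected, and a comparison of sections.

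**Inputs.**
- Go-live: 1 January 2018 (Sections 3c and 4a).
- 3-month call: 10–20 weeks (Section 4b).
- 9-month call: printed as 3555 weeks, read as 35–55 (Section 4b).
- Intervention dyads: 35. Doctors: up to 14.
- Assumption: the vote was in June 2017 and index visits follow it.

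**Which interviews fall after go-live?** The critical visit date is go-live minus the window limit.

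| Limit | Visit date at which it falls on 1 January 2018 |
|---|---|
| 10 weeks | 23 October 2017 |
| 20 weeks | 14 August 2017 |
| 35 weeks | 1 May 2017 |

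- 9-month call: any visit from 1 May 2017 has its whole window on or after go-live. A visit on 7 June 2017 gives 7 February to 27 June 2018, about 5 to 25 weeks after. A visit on 31 December 2017 gives about 35 to 55 weeks after.
- 3-month call: wholly before go-live for visits before 14 August 2017, straddling it for visits from 14 August to 22 October, and wholly on or after it from 23 October.

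So, if go-live happens as expected, every dyad seen between the assumed vote and the end of 2017 has notes open before its 9-month call.

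**How sensitive is this to the calendar?** Section 4b also says participation lasts no longer than 26 weeks, which conflicts with a 9-month call. Under a 26-week limit, dyads enrolled before 3 July 2017 (1 January 2018 minus 26 weeks) would finish before go-live. The repeated 9-month endpoint makes that reading less likely, but the two statements need reconciling in any case.

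**How many dyads?** The number of declining doctors is not stated. With equal caseloads (assumption), each accounts for at most:
- 14 doctors: 35/14 = 2.5 dyads; 2.5/35 = 7%.
- 7 doctors (illustrative): 35/7 = 5 dyads; 5/35 = 14%.

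The total runs from none, if no doctor declines, to all 35, if every doctor declines and every visit precedes go-live. If a fraction *p* of intervention dyads goes without the handout, the arm's mean effect falls by *p* times the handout's own contribution. One declining doctor therefore costs at most 7% (14 doctors) or 14% (7 doctors) of that contribution. The contribution itself is not given in the documents.

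**How do the sections fit together?** Section 4a's rule follows directly on the statement about go-live and couples education with access. The natural reading is that teaching is omitted while there are no notes to read. The *as relevant* condition on the handout points the same way for visits after go-live. It does not help dyads seen earlier, because it is tied to the single post-visit meeting.

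**Is there bias?** Blocking within doctor puts each doctor's dyads in both arms in near-equal numbers, so note opening is balanced. Controls who see open notes are receiving usual care, which is the stated comparator.

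**The case for a change.** The strongest argument for a change starts from the pilot's aim: whether a three-component package can be delivered. How many dyads received the third component is then a basic result. Respecting a doctor's choice explains the lack of teaching while notes are closed, but not the silence once they open. The recorded decision does not show when each doctor's notes opened or who received the handout. A clarifying clause, a date field for each doctor and a row of counts would cost little.

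Part of this stands. The text has no end date, and neither the switch-on date nor a count of handouts is planned. But the recorded decision, the visit date and the time-stamped MyChart records named in Section 7a largely show who should have been taught. An analyst describing delivery would use them without being told to. Writing this down adds detail and alters no result.

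Teaching the earlier dyads separately is harder to support:
- A handout mailed at go-live cannot affect the 3-month outcome for visits before 14 August 2017, because those calls are already over.
- Mailing adds a second mode of delivery, at a variable time after the visit, and so creates its own uneven exposure.
- A handout at the visit teaches a feature the dyad cannot yet use, and sits awkwardly with the doctor's decision.

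**Conclusion.** No change follows. The gap is real but small, and analysts can fill it sensibly by letting education follow the doctor's note status on the visit date. Dilution relative to a fixed three-component package is not a departure from this plan, which makes the third component conditional and says openly that some dyads will get two. What is missing for them is an informational handout within a brief meeting; the checklist, portal registration and MyChart handout remain.

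There is no bias between arms, and Section 7c plans no inferential testing, urges caution and uses effect sizes only to help plan a later trial. The number affected may be zero. It is at most 7% of the intervention arm per declining doctor with 14 doctors, or 14% with 7, assuming equal caseloads. The calendar rests on a June 2017 vote with visits after it. Later visits leave fewer dyads seen before go-live. The clash between the 26-week limit and the 9-month call is a separate inconsistency and does not alter this conclusion.

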**b. Secondary outcome variables.**

Secondary outcomes involve the following process measures: patient and doctor reports of family effectiveness in visit communication, patient and family satisfaction with the doctor, and reported quality of communication.

**c. Statistical plan including sample size justification and interim data analysis.** In this two-group randomized pilot trial, we will compare the effects of the intervention in the investigational arm on communication and outcomes for up to 70 patients (35 per group) with (a) advanced (stage IV) or (b) early (stage I-III) breast cancer (if receiving IV adjuvant systemic therapy) and their family member. As a Stage 1 developmental study of a complex behavioral intervention, the sample size is based on pragmatic considerations related to available resources, project duration, and study objectives. Analyses will be performed in SAS statistical software, with each patient-family dyad as the unit of analysis. We will rely on established cut-points and approaches to constructing outcome measures, as well as measures of patient and family attributes that will serve as control variables (sociodemographic characteristics, health status, aspects of the patient and family relationship, family role appraisal). We will stratify the study sample based on AJCC TNM staging (stage I-III or stage IV). We will primarily evaluate the consistency, direction, and magnitude of differences in study outcomes by undertaking analyses that are stratified by treatment group (intervention versus control arm) and for subgroups of patients by cancer stage (early or advanced stage). We will evaluate recruitment, retention, and the timeliness and completeness of collected data, as well as intervention acceptability (utility, burden, helpfulness) using questions from our formative work. We recognize the need for caution in interpreting pilot trial results. Therefore, inferential statistical testing is not planned in analyses of the pilot trial. However, we will evaluate recruitment and dropout rate as well as effect size of primary and secondary

outcomes to help inform the design and sample size calculations for a larger trial. **d. Early stopping rules.** None.

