This is a study of communication in breast cancer care. The study will evaluate a multicomponent intervention for patients with breast cancer and their family caregivers – each of the intervention components has been successfully tested and found to be acceptable. Adverse events that result from this study are unlikely. Unanticipated problems or adverse events will be reported promptly to the IRB by the PI. Study deviations will be documented and monitored in keeping with Good Clinical Practice in Social and Behavioral Research.
- d. **Legal risks such as the risks that would be associated with breach of confidentiality.**  
Participant privacy will be ensured by asking sensitive questions by telephone so that others who are present at the time of the survey are unable to hear the questions that are being asked. Research staff will assist patient participants in completing study surveys and questions that are asked in person will not involve sensitive topics. Pre-consultation consent and post-visit surveys for patients and family participants will typically be completed in a private room proximal to the clinic waiting room for additional privacy. Information collected from patients and families will not be shared with one another.

e. **Financial risks to the participants.** None

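### Alternating block sizes within small doctor strata are a fixed pattern; random, undisclosed sizes would reduce certain foreknowledge of assignments at almost no cost

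*Combined protocol and SAP*

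**What the plan says.** Section 4.a allocates dyads "in a 1:1 ratio using stratified, blocked randomization by doctor with alternating block sizes". On the number of strata it says "We expect to enroll up to 14 medical oncologists in this study", and on the number of participants "for a total of 70 patients and 70 family members". The protocol does not give the block sizes, say which size comes first, say who holds the list, or describe how upcoming assignments are concealed.

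The same section has a member of the research team meet each dyad in the waiting room before the visit. Intervention dyads then meet with "research staff to receive a copy of the patient-family agenda-setting checklist", and research staff help with portal registration after the visit. Section 4.b places written consent at this in-person encounter, and section 8.d adds: "Pre-consultation consent and post-visit surveys for patients and family participants will typically be completed in a private room". Section 4.a puts randomization after consent and requires both members of the dyad to consent.

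Section 4.c calls the study team blinded. That can describe the masked telephone interviewers, but not the staff who hand over the checklist.

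**The concern.** Varying the block size is meant to stop people who see past assignments from working out where a block ends. A strict alternation does this only while its sizes and order stay unknown. Once they are known, every block boundary in a doctor's sequence can be located, and the assignments at the end of each block are determined.

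This matters here because the staff on site see which dyads receive the checklist, and nothing in the documents says that a different person screens, recruits or takes consent. Someone who knew the next arm could, even without intent, press one dyad harder than another. The primary outcomes come from surveys of unblinded dyads, and section 7.c uses the effect sizes and the recruitment and dropout rates to design a larger trial.

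**Working it through.** The plan states no predictability figure to reproduce. Its counts agree with each other: section 7.c gives "for up to 70 patients (35 per group", and 35 + 35 = 70.

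**Inputs from the documents.** Up to 70 dyads, up to 14 oncologists, 1:1 allocation, blocks within doctor. Mean stratum size is 70/14 = 5. If only 7 oncologists contributed it would be 70/7 = 10.

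**Assumptions, because the documents are silent.** Block sizes 2/4 or 4/6; equal strata; an observer who knows the set of sizes and all past assignments for that doctor. For the random scheme, each block's size is drawn independently with equal probability.

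**Certain assignments per block.** In a block of size 2k with known boundaries, the next assignment is certain once one arm has used its k places. The expected number of certain assignments per complete block is 2k/(k+1):
- size 2: 1
- size 4: 1/3 (third place) + 1 (fourth) = 4/3
- size 6: 0.1 (fourth place) + 0.4 (fifth) + 1 (sixth) = 1.5

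**Alternating, sizes and order known, 5 dyads per doctor.**
- 2 then 4: (1 + 1/3)/5 = 26.7%, or 18.7 of 70
- 4 then 2, and 4 then 6: (1/3 + 1)/5 = 26.7%
- 6 then 4: (0.1 + 0.4)/5 = 10.0%, or 7.0 of 70

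Fixed blocks of 4 also give (1/3 + 1)/5 = 26.7%. A known alternation can therefore protect no better than a single block size.

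**Alternating, sizes and order known, 10 dyads per doctor.**
- 2 then 4: (1 + 4/3 + 1)/10 = 33.3%
- 4 then 2: (4/3 + 1 + 4/3)/10 = 36.7%
- 4 then 6, or 6 then 4: (4/3 + 1.5)/10 = 28.3%

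**Random draw, 5 dyads per doctor.**
- Sizes 2/4: certainty arises at place 3 with probability 1/6, at place 4 with 1/6 and at place 5 with 1/12. The share is (5/12)/5 = 8.3%, or 5.8 of 70.
- Sizes 4/6: (½ × 0.1 + ½ × 0.4)/5 = 5.0%, or 3.5 of 70.

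The remaining entries come from exact enumeration of all sequences. Share of assignments known with certainty:

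| Dyads per doctor | Sizes | Alternating, order known | Alternating, start unknown | Random draw |
|---|---|---|---|---|
| 5 | 2/4 | 26.7% | 10.0% | 8.3% |
| 5 | 4/6 | 26.7% (4 first), 10.0% (6 first) | 5.0% | 5.0% |
| 10 | 2/4 | 33.3% (2 first), 36.7% (4 first) | 21.1% | 9.6% |
| 10 | 4/6 | 28.3% | 18.7% | 6.0% |

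Share guessed correctly by always choosing the likelier arm:

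| Dyads per doctor | Sizes | Alternating, order known | Alternating, start unknown | Random draw |
|---|---|---|---|---|
| 5 | 2/4 | 66.7% | 66.7% | 67.5% |
| 5 | 4/6 | 66.7% (4 first), 62.0% (6 first) | 64.3% | 64.3% |
| 10 | 2/4 | 70.0% (2 first), 71.7% (4 first) | 70.8% | 71.5% |
| 10 | 4/6 | 69.3% | 69.3% | 67.9% |

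**Balance.** Expected absolute imbalance within a doctor is 1.00 dyad under every scheme shown at 5 per doctor. At 10 per doctor it moves by less than half a dyad: from 0.67 or 0.00 to 0.23 for sizes 2/4, and from 0.00 to 0.38 for sizes 4/6.

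**The case against.** The strongest reply is that the exposure is conditional and narrow. The protocol gives neither sizes nor order and does not say that staff will have them. Alternating may be loose wording for varying. If staff do not know the starting size, then at 5 dyads per doctor random sizes gain 10.0 − 8.3 = 1.7 points for 2/4 and nothing for 4/6. Small blocks within doctor drive general guessability, and randomizing the sizes hardly changes it; in some 2/4 cases the best guess does slightly better.

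The route to selection is also limited. Letters go out before visits that are already scheduled, both members must consent before randomization, and nothing suggests that research staff can move oncology appointments. Follow-up interviewers are masked. Section 7.c says that "the sample size is based on pragmatic considerations related to available resources" and that "inferential statistical testing is not planned in analyses of the pilot trial", so no test result is at risk.

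Most of this stands and sets the size of the point. It does not remove it. Consent before randomization does not help if the person conducting the consent discussion already knows the next arm, and the documents describe no concealment that would prevent this. The gain is also substantial at 10 dyads per doctor even with an unknown start: 21.1% to 9.6% for 2/4 and 18.7% to 6.0% for 4/6. If random variation was intended, the edit only says so.

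A reader might infer that staff will in fact know upcoming assignments, or that the pilot's effect sizes are biased. The documents support neither. The first requires staff to learn the sizes and order. For the second, a share of certain assignments is not an estimate of bias, and nothing in the documents allows one to be derived.

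**Conclusion.** The point holds as a small improvement to a stated method. The literal rule is a fixed pattern in strata of about 5 dyads, used where the staff who see past assignments are not separated from those who recruit. Under assumed sizes of 2/4 or 4/6, with sizes and order known, certain foreknowledge falls from 10-27% to 5-8% of assignments at 5 per doctor, and from 28-37% to 6-10% at 10 per doctor. With the start unknown, the fall at 5 per doctor is 0-2 points.

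It would be wrong to conclude that random sizes make the allocation unpredictable: best-guess success stays at about 62-72%. What is removed is certainty. These figures rest on the assumed block sizes, equal strata, and an observer who has seen every earlier assignment for that doctor.

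**What to change.** In section 4.a, replace the alternating rule with a statement that block sizes are drawn at random and are not disclosed to recruiting or intervention staff. Add that the list is generated and held by someone not involved in recruitment. Randomization after both members consent is already in section 4.a and need not be added.

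The cost is a sentence or two of protocol text and a regenerated list, applied only to assignments not yet released if recruitment has begun. The sample size and the 1:1 ratio do not change.
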